7.9.5 Indeterminate imaging outcome

If the imaging is indeterminate and not clearly abnormal, the following scenario would apply:

- If imaging is indeterminate at T0, the participant will continue the study and undergo T1 visit. Subsequent follow-up imaging (as part of MDT decisions) reports will be collected as part of study data.
- If indeterminate at T1, imaging reports will be collected as part of study data and participant will undergo T2 visit. Cancer and mortality registry records will be reviewed as planned.
- If indeterminate at T2, imaging reports will be collected as part of study data. Cancer and mortality registry records will be reviewed as planned.

7.10 DEFINITION OF BIOPSY OUTCOMES

The categories of clinical diagnostic follow-up findings are defined as follows:

- Histologic findings show pancreatic cancer, any stage (I-IV) based on American Joint Committee on Cancer (AJCC) v8.0.
- Histologic findings are indeterminate
- Histologic findings are consistent with pre-neoplastic lesions (IPMNs, mucinous cystadenoma or with pancreatic intraepithelial neoplasia (PanINs)).
- Histologic findings are consistent with an inflammatory process (benign disease)

Overall, the reference method will be histopathologic confirmation of PC, and/or definitive imaging diagnosis of PC.

7.11 DEVELOPMENT OF OTHER CANCER TYPES AND INCIDENTAL FINDINGS

In the event of any significant incidental findings on imaging, the participant would be informed of such findings by the local PI and study team, who will also inform their GP with any follow up recommendations by the local MDT as per usual clinical care.

For participants diagnosed with other cancers unrelated to the pancreas or other incidental findings during the study, pathology reports and imaging will be collected when available.

Participants diagnosed with other cancer types will discontinue further Avantect tests. Cancer and mortality registry searches will occur as planned.

7.12 TRIAL INTERVENTION DISCONTINUATION AND PARTICIPANT WITHDRAWAL

Participants with abnormal imaging results (cancer diagnosis) will discontinue further study visits but cancer and mortality registry searches will be completed as planned.

Participants will be able to withdraw from the study at any time and this will be recorded on the study database. It should be ascertained and documented whether the participant wishes to;

1. withdraw from future study procedures but allows for new data/information to be collected and already collected data and samples to be retained for analysis.
2. withdraw from future study procedures including collection of new data but allows for already collected data and samples to be retained for analysis.
3. completely withdraw, i.e. withdraw from future study procedures and requests that any remaining samples are disposed of and no further data will be collected.

A complete withdrawal from the trial should be recorded as end of study for the participant in the relevant eCRF and in their medical record and no further data should be collected for this participant. Already collected data will be retained to protect the validity of the study in line with HRA guidance.

If participants withdraw consent for further study procedures but are willing to continue sharing information it would remain useful for the trial team to continue to collect any routine data (i.e., data that can be collected with no impact on the participant beyond standard clinical care/follow-up), and this will continue unless the participant explicitly requests otherwise.

In any case, participants who completely withdraw or withdraw only from further study procedures should revert to standard clinical care/follow-up as deemed by the responsible clinician.

8. SAFETY

8.1 DEFINITIONS

Standard BS ISO 20916:2019 (in combination with the UK Medical Device Regulations 2002, as amended) provides the following definitions relating to adverse events in medical device trials:

Device deficiency
	
Inadequacy of an investigational medical device with respect to its identity, quality, durability, reliability, usability, safety or performance.
 
Device deficiencies include malfunctions¹, use errors², and inadequacy in the information supplied by the manufacturer including labelling.
 
These include deficiencies related to both the investigational medical device, or the comparator

Adverse Event (AE)
	
Any untoward medical occurrence, inappropriate patient management decision, unintended disease or injury or any untoward clinical signs (including an abnormal laboratory finding) in subjects, users or other persons with any connection to study related activities, whether or not related to the IVD medical device under investigation (and whether anticipated or unanticipated).
 
Adverse events can be cause by e.g. insufficient or inadequate instructions for use, deployment, installation, operation, or any malfunction or deterioration of the IVD medical device under investigation. This includes events related to the investigational medical device or comparator. For subjects, this includes events related to all procedures involved. For users or other persons, this is restricted to events related to the use of investigational medical devices.
 
False negative or false positive results are not considered adverse events unless inappropriate patient management decisions are made based on those false results.

Serious Adverse Event (SAE)	
Any adverse event that led to any of the following:
 
 • Death • A life-threatening illness or injury • A permanent impairment of a body structure or body function including chronic diseases • In-patient or prolonged hospitalisation • Medical or surgical intervention to prevent a life-threatening illness or injury or permanent impairment to a body structure or a body function • Foetal distress, foetal death, a congenital abnormality, or birth defect including physical or mental impairment 
Planned hospitalisation for a pre-existing condition, or a procedure required by the Clinical Performance Study Protocol without serious deterioration in health, is not considered a serious adverse event

Adverse Device Effect (ADE)	
Adverse event related to the use of an IVD medical device under investigation.
 
This includes any adverse event resulting from insufficient or inadequate instructions for use, installation, operation, or any malfunction of the IVD medical device under investigation. This includes any event resulting from use error or from intentional misuse of the IVD medical device under investigation.

Serious Adverse Device Effect (SADE)	
Adverse device effect that has resulted in any of the consequences characteristic of a serious adverse event.

Anticipated Serious Adverse Device Effect (ASADE)	
Serious adverse device effect (SADE) which by its nature, incidence, severity, or outcome has been identified in the manufacturers' risk analysis report, and listed in either the clinical performance study protocol, or Investigator brochure.

Unanticipated Serious Adverse Device Effect (USADE)	
Serious adverse device effect (SADE) which by its nature, incidence, severity, or outcome has not been identified in the risk analysis report, and listed in either the clinical performance study protocol, or Investigator brochure.

1. *failure of an investigational medical device to perform in accordance with its intended purpose when used in accordance with the IFU, CPSP, or IB*
2. *act or omission of an act that results in an IVD medical device output which differs from that intended by the manufacturer or expected by the user:*
 - a. *includes the inability of the user to complete a task*
 - b. *users may or may not be aware that a use error has occurred*
 - c. *can result from a mismatch between the characteristics of the user, the user interface, task, or use environment*
 - d. *an unexpected physiological response of the subject is not by itself considered use error*
 - e. *a malfunction of an IVD medical device that causes an unexpected result is not considered a use error*

8.2 TRIAL SPECIFIC REQUIREMENTS

8.2.1 Adverse Events

a) Recording in medical notes:

All Adverse Events (AEs) from the date of informed consent to the end of participation in the trial should be recorded in the *patient's medical notes* as per usual practice.

b) Recording in trial database:

The following adverse events are expected and do not require reporting in the eCRF. However:

- 1) if they are continued for more than one week, then these should be entered as adverse events in the eCRF, *or*
 - 2) if the event meets the criteria of 'serious' as defined in section 8.1, then it must be reported in the eCRF and should also follow the process for reporting as a Serious Adverse Event
- **Related to blood collection:**
 - Pain, bleeding, bruising, swelling, or haematoma at site
 - low blood pressure
 - fainting at time of collection
 - headache
 - blood clot formation
 - infection at the site where skin is punctured by the needle (very rarely)
 - **Related to MRI or CT:**
 - Allergic reaction to contrast
 - nausea due to contrast
 - panic attack
 - abdominal pain
 - contrast reactions (incl. contrast-induced nephropathy [CIN], acute kidney injury [AKI]) in subjects with pre-existing kidney failure

Any other adverse events that are considered related to the study procedures (blood collection and imaging) and occurring within 7 days of each visit (excl. T3) must be recorded in the eCRF.

Events with an onset occurring after 7 days post-visit should not be recorded as AEs in the eCRF.

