5. SELECTION AND ENROLMENT OF PARTICIPANTS

5.1 PARTICIPANT ENROLMENT

Participants will be approached to take part in SAFE-D via their GP or SDSC. Electronic Health Record (EHR) searches will be undertaken by the study team at participating GP practices and subjects with a recent diagnosis of DM (within six months) will be eligible for enrolment. Subjects attending SDSCs will also be eligible for enrolment. In addition, participants may self-refer for the study via the SAFE-D booking website. Participants who sign the consent form will be considered enrolled.

The study is expected to enrol 15,000 participants over 36 months, including a six-month pilot study to evaluate recruitment feasibility and to estimate the number of participating sites required, and an interim analysis for futility and efficacy (Stage 1). Participants will remain in the study for 12 months, attending study visits at enrolment (baseline (T0)) and at six (T1) and 12 months (T2) post enrolment. There may be planned recruitment stops between the Pilot and Stage 1 of the study to allow for a data driven 'stop-go' decision should this decision not be concluded in the lead up to Stage 1. Recruitment will continue once the Stage 1 interim analysis requirements have been met and will continue unless that analysis concludes that the intervention is futile. Total study duration is expected to be 7 years including 12 months for analysis and report writing.

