6.1 SAMPLE HANDLING

At each study timepoint 2x10 mL Streck® tubes and 1x6 mL lithium heparin tube will be collected from participants. The 2x10 mL Streck® tubes will be used for the Avantect test or future research depending on the study arm, and 1x6 mL lithium heparin will be used for the evaluation of a pancreatic cancer metabolomic signature.

All blood samples will be posted overnight according to Laboratory Manual using study specific boxes equivalent to Royal Mail Safeboxes, to the agreed laboratory: University of Southampton WISH Laboratory. Samples will be sent from sites pseudo-anonymised and fully labelled with a patient and time-point specific kit ID number together with a test requisition form allowing for patient specific reconciliation once received at the WISH laboratory. All sites will keep a record of all samples collected, stored, and shipped. A detailed Laboratory Manual will be provided to sites which will include details regarding sample preparation, handling, shipping and tracking.

In the event of postal delays, any Streck sample received at WISH laboratory after seven days from date of blood collection will be deemed unsuitable for Avantect testing and participants may be asked to undergo repeat blood draw. If repeat T0 draw is requested it must be completed while the participant is still within 6 months from diabetes diagnosis. If T1 or T2 repeat blood collection is requested, it must be within 28 days of the initial sample collection date. A repeat draw can also be requested if a sample is damaged during transport.

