Streck® tubes will be processed to plasma within 24 hours of receipt in the WISH laboratory by trained operators and shipped at agreed frequencies as per the Laboratory Manual to ClearNote Health centralised laboratory (San Diego, California, USA). Streck plasma samples collected from patients randomised to the intervention arm will be analysed and results will be generated within 14 business days of receipt of arriving at Clearnote Health and “detected” test results will be reported to SCTU team by providing Avantect test results via an excel file and individual patient reports via secure file sharing (Safesend.soton.ac.uk). In the event of a sample failing predefined Avantect metrics, (expected failure rate is ~4%), the participant will be asked to return for a repeated draw (if the participant is still within the 28 days time frame from the original blood draw). If the failure happens at T0 and no blood could be collected while the participant is still within 6 months of diabetes diagnosis timeframe the participant will be asked to come back at T1. If the failure happens at T1 or T2 and no re-draw was performed, the participant will remain in study. For participants assigned to the control arm, samples will be kept for future potential Avantect testing and/or future research.

Lithium heparin samples will be processed according to SAFE-D specific SOP at the WISH laboratory and stored for future research within the SAFE-D study (or future ethically approved research).

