8.5.1.4 Reporting Timelines

All reportable AEs and SAEs should be reported from the date of informed consent up to 7 days after each study procedure.

All unresolved adverse events should be followed by the investigator until one of the end of trial criteria is met (i.e. lost to follow up, withdrawal etc.). At the last scheduled visit, the investigator should instruct each participant to report any subsequent event(s) that the participant, or the participant’s general practitioner, believes might reasonably be related to participation in this trial. The investigator should notify the trial sponsor of any death or adverse event occurring at any time after a participant has discontinued or terminated trial participation that may reasonably be related to this trial.

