9.3 STUDY TIMEPOINTS

There will be three timepoints for blood collection: at baseline (T0), 6 months +/- 2 weeks post-baseline (T1), and 12 months +/- 2 weeks from baseline (T2). For each study timepoint, the Avantect test will be conducted. For samples collected from participants assigned to the intervention arm, the Avantect test will be assessed as soon as possible within 14 business days of receipt of samples in the analysing laboratory at ClearNote Health. Those with positive test results (test result = Avantect “detected”) in the intervention arm will undergo diagnostic pancreas imaging. Samples collected from participants assigned to the Control arm will be stored for potential future Avantect testing or future research.

The study design comprises a pilot and two study stages:

- Stage 1 Analysis will be carried out 6 months after the T1 visit for 3,200 participants in the intervention arm. Only participants followed up for a minimum of 6 months after the T1 visit in the intervention arm will be included in this analysis.
- Stage 2 Analysis will be carried out after 3-year follow-up data has been collected for all 15,000 participants.

In addition, during the study annual readouts will be provided to the data monitoring committee to monitor study progress and inform on decisions to continue or stop the study.

The diagnostic performance of the Avantect test results will be summarised according to the pancreatic cancer diagnoses collected by the point of analysis. The stage shift, and resection rate of pancreatic cancer will be summarised by arm. For this purpose, a positive test at any timepoint will be considered a ‘positive prediction’ e.g., if a participant has a negative result at T0, but a positive result at T1, their overall prediction will be considered as at-risk of pancreatic cancer.

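### The eCRF adverse-event window in section 8.2.1 runs from each visit, so it will normally close before the imaging whose events it is meant to record, and it conflicts with section 8.5.1.4

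*Protocol*

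**What the plan says.** **Section 8.2.1** sets out which adverse events enter the trial database.

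- It first lists reactions expected after blood collection and after MRI or CT. These stay out of the eCRF unless they last more than a week or are serious.
- It then covers every other event "considered related to the study procedures (blood collection and imaging) and occurring within 7 days of each visit (excl. T3) must be recorded in the" trial database.
- It closes with a bar: "Events with an onset occurring after 7 days post-visit should not be recorded as AEs in the eCRF".

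**Visits** are defined in section 5.1, which has participants "attending study visits at enrolment (baseline (T0)) and at six (T1) and 12 months (T2) post enrolment". The schedule in section 7.1 adds only T3, a registry review, and 8.2.1 leaves T3 out of the window. Imaging appears in neither place.

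**Imaging** is triggered by a detected result in the intervention arm (sections 7.8.1 and 9.3). The site notifies the participant and the GP and makes an urgent referral to the local hepatobiliary (HPB) service, which schedules the scan.

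**Timing before the result** is in section 6.1. "All blood samples will be posted overnight according to Laboratory Manual"; the Streck tubes "will be processed to plasma within 24 hours of receipt in the WISH laboratory by trained operators and shipped at agreed frequencies" to San Diego; and "results will be generated within 14 business days of receipt of arriving at Clearnote Health". Section 9.3 repeats the limit: "within 14 business days of receipt of samples in the analysing laboratory".

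**Section 8.5.1.4** gives a different window: "All reportable AEs and SAEs should be reported from the date of informed consent up to 7 days after each study procedure". **Section 8.5.1.1** says that related events are entered in the eCRF under the requirements of section 8.2.

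**The concern.** Section 8.2.1 treats imaging as a study procedure whose related events have to be recorded, but starts the clock at the blood-draw visit. The scan comes at the end of a chain that starts with that visit, so the clock is likely to have run out before the participant is scanned. The closing sentence of 8.2.1 then goes beyond not asking for the event: it tells the site to leave it out.

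A site that reads 8.5.1.4 would count from the scan and could record the same event. Sites may therefore handle identical events differently.

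Imaging is the main physical consequence of a positive test, and section 1.3.1 names a false result as the primary risk of the test. Study-triggered imaging happens only in the intervention arm. The monitoring committee is to watch safety (section 13.3), and section 16.2 plans no source data verification at sites, so an event held only in the medical notes would not routinely reach the trial dataset.

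**Working it through.** No stated figure needs reproducing for the window itself. The check is a timeline, followed by a check of scale.

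**Inputs**

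| Step | Duration | Source |
|---|---|---|
| Visit | day 0 | 5.1 |
| Post to the processing laboratory | about 1 day | 6.1 |
| Processing to plasma | up to 1 day | 6.1 |
| Shipment to San Diego | not stated; **assumed 1 to 7 days** | 6.1 gives only agreed frequencies |
| Assay | up to 14 business days | 6.1, 9.3 |
| Report, notification, referral, scan | no durations given | 6.1, 7.8.1 |

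**Business days to calendar days.** Ten business days are 14 calendar days. The other four take 4 calendar days if no further weekend intervenes and 6 if one does. So 14 business days are 18 to 20 calendar days, depending on the weekday of receipt.

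**Day of the result at the permitted limits** (post + processing + shipment + assay):

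- 1 day of shipment: 1 + 1 + 1 + 18 = day 21, to 1 + 1 + 1 + 20 = day 23.
- 7 days of shipment: 1 + 1 + 7 + 18 = day 27, to 1 + 1 + 7 + 20 = day 29.

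That is about three to four times the window (21/7 = 3.0; 29/7 = 4.1), before notification, referral and scan.

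**Time left if the assay is much faster than its limit.** With 1 day of post, 0 to 1 day of processing and 1 day of shipment, 7 − (1 + 0 + 1) = 5 or 7 − (1 + 1 + 1) = 4 days remain. The assay, report, notification, referral, scan and onset of the event would all have to fit into them. With 7 days of shipment the remainder is negative: 7 − (1 + 0 + 7) = −1 or 7 − (1 + 1 + 7) = −2.

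**Which section governs.** For the same non-serious event two days after a scan:

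- 8.2.1 counts from the visit, so the event is late and is to be left out.
- 8.5.1.4 counts from the procedure, so the event is in time.
- 8.5.1.1 refers eCRF entry of related events back to 8.2. Section 8.5.1.4 itself speaks only of reportable events. It therefore does not clearly override the bar.

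**Which events are affected**

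| Non-serious imaging-related event | Intended for the eCRF by 8.2.1? | Lost to the window? |
|---|---|---|
| Listed reaction, one week or less | No, exempt by design | No |
| Listed reaction, more than one week | Yes | Yes, if onset is after day 7; the bar has no exception |
| Unlisted | Yes | Yes, if onset is after day 7 |

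**Scale.** Section 9.2 has 73 cancers and 7,239 participants without cancer in the intervention per protocol group, with 65% sensitivity and 95% specificity. Expected detected results are 0.65 × 73 + 0.05 × 7,239 = 47.45 + 361.95 = 409.4. The protocol's rounded cells give 48 + 362 = 410, or 410/7,312 = 5.6% of that group, of whom 362 are false positives.

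**The case against.** The strongest reply is that the protocol keeps most imaging reactions out of the eCRF on purpose. The MRI and CT list covers contrast allergy, nausea, panic attack, abdominal pain and, in participants with pre-existing kidney failure, contrast reactions including kidney injury. These need no entry unless prolonged or serious, whatever the window. That stands. A reader might infer that the window removes practically all non-serious imaging events, or that close to none would be eligible. The documents do not support this, because much of the absence comes from the exemption and would remain after the window is mended.

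Other safeguards also stand. All adverse events go in the medical notes (8.2.1). Serious events are reported whether or not they are related (8.2.3). Section 8.5.1.4 provides for follow-up of unresolved events and for notice of later events reasonably linked to the trial. No endpoint in section 2.4 counts non-serious adverse events.

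Two further inferences go too far. One is that a scan cannot fall inside the window: 14 business days is a maximum, no minimum is given, and a much delayed scan could by chance fall within seven days of the next visit. The other is that all 410 would be imaged: section 7.8.1 provides for participants who are unable or unwilling, so 410 is an upper figure for imaging.

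None of this removes the conflict. Medical notes are not the trial dataset, and capture that depends on a coincidence of dates is not what 8.2.1 sets out to do.

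**Conclusion.** The point holds as an internal inconsistency with a limited practical effect. The window in 8.2.1 largely defeats that section's own imaging clause, and it disagrees with 8.5.1.4 on where the seven days start.

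The events at risk are non-serious and imaging-related: those not on the expected list, and listed MRI or CT reactions that last more than a week. They would arise among up to about 410 intervention participants referred for imaging, some 362 of them false positives. How many events that means cannot be stated, because the protocol gives no event rate.

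The timeline rests on the turnaround limits in sections 6.1 and 9.3 and on an assumed 1 to 7 days of shipment. The conclusion is insensitive to the shipment figure: at the assay limit, the assay alone takes 18 to 20 calendar days against a window of seven. It would weaken only if results regularly came back within a few days of the visit, which nothing in the protocol suggests.

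**What to change.** Reconcile 8.2.1 and 8.5.1.4. In 8.2.1, replace the visit as the anchor with each study procedure, defined as a blood draw or study-triggered imaging, both in the requirement to record and in the closing bar. Section 8.5.1.4 already uses this anchor. Add the imaging date to the data collected, so that the window can be checked. The exemption for short-lived expected reactions can stay as it is; the change does not touch it.

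The cost is a wording amendment, one date field and a few more adverse-event entries. There is also some work in passing information from the local HPB service, where the scan takes place, to the recruiting site that completes the eCRF.
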